### **Frequency and Duration of Follow-Up:**

Patient characteristics and demographic information were collected at baseline. All patient-reported outcome measures are being collected at baseline, 6 weeks, and 3, 6, 9, and 12 months from the initial visit, with the primary comparison at 12 months. Patient satisfaction, global rating of change, adverse effects, and healthcare utilization are being collected at follow-up time points only. Patient adherence to PT recommendations is being collected at the 6-week follow-up.

### **Participant Characteristics:**

The following characteristics and demographic information were collected from patients at baseline: age, first three digits of their postal code (to determine rural/urban status), biological sex, gender, identification as a member of a racialized group, duration of the current episode of LBP, previous history of LBP, number of other pain locations, highest level of education achieved, household income, and work status. In addition, the following questionnaires were administered at baseline as potential covariates and to inform subgroup analyses as part of our process evaluation.

Functional Comorbidity Index: an 18-item list of comorbidities that are associated with physical functioning. Each comorbidity is assigned a score of 1 and the total score is the sum of the comorbidity elements.

Keele STarT Back Tool: categorizes patients with LBP into low, medium, or high risk of persistent pain and disability based on physical and psychosocial risk factors.

### **Patient Health and Experience Outcomes:**

Self-Reported Disability (Primary Outcome): using the RMDQ, which demonstrates reliability, validity, and responsiveness in people with acute and chronic LBP.

Pain Intensity: using a Numeric Pain Rating Scale (0-10) for pain at rest, pain when walking, and pain when lifting a bag of groceries from the floor. Each will be reported on a scale of 0 (no pain at all) to 10 (worst imaginable pain).

Health-Related Quality of Life: using the EuroQOL-5D (EQ-5D-5L), which demonstrates good reliability and validity, and is suitable for economic evaluation in LBP. The EQ-5D-5L VAS score (0-100) will be reported as a patient health outcome. The EQ5D responses will be converted to an EQ5D index value using the value set calculated for the Canadian context. The index value will be reported as a patient-level health outcome and will also be used to calculate quality-adjusted life years (QALY) for our outcome in the economic evaluation.

Global Rating of Change: using an 11-point global rating of change scale, from a great deal better (+5) to a great deal worse (-5), as has been recommended for self-reported rating of change.

Participant satisfaction: using an 11-point scale for satisfaction with care, extremely dissatisfied (-5) to extremely satisfied (+5).

Adverse events: using an adverse events questionnaire consistent with reporting guidelines that asks: 1) if the patient participant has experienced any adverse event(s) as a result of any of the treatments received; 2) what adverse event(s) were experienced; 3) how long the event(s) lasted; and 4) how severe each adverse event was. For analysis, adverse events will be identified as serious or non-serious. An adverse event will be identified as serious if any of the following criteria are met: the participant requires in-patient hospitalization or an emergency department visit due to the adverse event,

the adverse event results in significant and persistent disability (beyond 72 hours), or the adverse event is life-threatening or results in death. These responses are being monitored as they are completed in order to provide ongoing oversight of patient participant safety.

The following measures will be assessed as secondary outcomes, reported in the trial results, and included in the process evaluation as potential mechanisms through which the PT-led primary care model influences LBP-related disability.

**Self-efficacy:** confidence in abilities to participate in usual activities using the Pain Self-Efficacy Questionnaire (PSEQ)

**Psychosocial risk factors for persistent pain and disability:** The Pain Catastrophizing Scale (PCS), Tampa Scale of Kinesiophobia 11 (TSK-11), and 2-item Patient Health Questionnaire (PHQ-2) will measure psychosocial factors associated with pain-related disability.

### **Health System and Societal Outcomes:**

Primary care physician or nurse practitioner encounters: the number of new and repeat primary care physician or nurse practitioner visits for LBP per patient. This measure will be considered a proxy for a potential increase in primary care team capacity achieved if the LBP-related workload of primary care physicians or nurse practitioners is reduced, thus increasing their availability to provide care to other patients.

Healthcare utilization within the primary care team: using data being collected from the EHR: consultations with other primary care team members (e.g., physicians, nurse practitioners, nurses, social workers, and occupational therapists) and group programming accessed within the primary care organization.

Healthcare utilization outside of the primary care team: using self-report data from follow-up surveys cross checked with reports the electronic health record when possible: medications used; walk-in clinic visits; ED visits; inpatient hospital stays; surgeries, injections, and other interventional procedures; visits to specialist physicians; diagnostic imaging; and visits to other health professionals outside the primary care team (e.g., chiropractors, massage therapists, occupational therapists, physiotherapists, chronic pain clinics).

Missed Occupational Activities: using self-report data from follow-up surveys: time (days) lost from paid employment, volunteer, homemaking, or educational activities related to LBP.

Assistance required: using self-report data from follow-up surveys: paid and unpaid assistance required. For example, self-care (e.g., taking medications, dressing/undressing, going to the bathroom, bathing/showering, grooming), shopping/groceries, meal preparation, housework, managing finances, or transportation (e.g., to a medical appointment).

Costs: Total costs per person will be calculated by summing direct healthcare costs and indirect costs using a human capital approach for missed occupational activities. Sources of direct healthcare cost data: Intervention costs will include the PT salary and training needed to carry out the intervention. Costs for publicly funded healthcare services will be obtained from the Ontario Ministry of Health Schedule of Benefits. Medication costs will be obtained from the Ontario Drug Benefit formulary. Expenses related to health services funded by private insurance or out of pocket will be collected through self-report at all follow-up assessments. Other costs incurred by the participant related to their LBP are also being collected by self-report, including support or assistance for self-care, housework,

shopping, or transportation (e.g., to healthcare appointments). The total direct costs will be determined by multiplying the quantity of resource use by the corresponding unit cost, summing the total cost over each follow-up interval, and then calculating the mean cost at each follow-up time point, as well as an overall mean cost for the entire study period. *Indirect costs:* Non-healthcare costs will be limited to loss of productivity using a human capital approach. The mean provincial wage reported by Statistics Canada will be used to assign a monetary value to time lost from paid employment. The minimum wage value in Ontario and BC will be used to place a value on time lost by those who were retired and time lost from volunteer, homemaking, caregiving, or educational activities.

**Cost effectiveness:** We will conduct a cost-utility analysis from both societal (primary) and health payer (secondary) perspectives to meet the needs of all knowledge users. For both societal and health payer perspectives, we will estimate the incremental cost-per-QALY gained.

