Primary care physician or nurse practitioner visits will be presented as rates and compared using rate ratios with adjusted Poisson or negative binomial regression. Other healthcare utilization within the primary care team (whether there were any other consultations with interprofessional team members and whether or not there was group programming accessed), and healthcare utilization outside of the primary care team (medications, diagnostic imaging, walk-in clinic visits, ED visits, specialist physician visits, emergency department visits, hospital admissions, interventional procedures, surgeries, other health provider visits) will be presented as incidence rates and compared by calculating relative risks with confidence intervals using robust Poisson regression, accounting for clustering. These models will use time as an offset to account for variable follow-up times and will incorporate empirical covariance (“sandwich”) bias-adjusted (residual-based) estimators and the Fay and Graubard correction to account for small number of clusters. Time (days) lost from occupational activities (paid employment, volunteer, homemaking, or educational activities) and assistance required (hours of paid assistance, hours of unpaid assistance) due to LBP will be presented as rates and compared using rate ratios with negative binomial regression.

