#### Economic evaluation

We will estimate the cost-effectiveness of the PT-led care model from both a societal (primary) and health system payer (secondary) perspective to meet the needs of all knowledge users. The total costs will be determined by multiplying the quantity of resource use (or lost days) by the corresponding unit cost (or hourly wage), summing the total cost over each follow-up interval, and then calculating the mean cost at each follow-up time point, as well as an overall mean cost for the entire one-year study period. Results will be presented as aggregated and disaggregated costs. Utility data will be generated using EQ-5D-5L index values (ie. utility scores) from all follow-up assessment time points. We will estimate QALYs for every participant, using the area under the curve approach, assuming linear interpolation between the measurements. To accommodate the hierarchical structure of the data, we will use bivariate multilevel modeling to estimate the incremental cost-effectiveness ratio using a calculation of cost-per-QALY gained for PT-led primary care versus usual care and to estimate the incremental net benefit at various willingness to pay values. To account for clustering of study sites, as well as heterogeneity in costs and treatment effect across jurisdictions, we will model treatment group as

a fixed effect and the study site a random effect; adjusting for the same covariates as the primary analyses as fixed effects in our models. We will conduct a probabilistic sensitivity analysis using 10,000 Monte Carlo simulations to present the uncertainty in our cost-effectiveness estimates. Simulation results will be plotted on cost-effectiveness planes and we will generate cost-effectiveness acceptability curves to display the probability that the PT-led care model is cost-effective across a range of willingness to pay thresholds.

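### The primary (societal) cost rule limits non-healthcare costs to lost productivity, so read literally the unpaid assistance hours get no price, and the rule contradicts the paid assistance and transport costs listed just before it

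*Combined protocol and SAP*

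**What the plan says.** All references are to the combined protocol and SAP.

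- **Perspective.** Under Health System and Societal Outcomes: "We will conduct a cost-utility analysis from both societal (primary) and health payer (secondary) perspectives". The Economic evaluation section repeats that the societal perspective is primary.
- **Total cost.** The Costs entry states: "Total costs per person will be calculated by summing direct healthcare costs and indirect costs using a human capital approach for missed occupational activities".
- **Limit on other costs.** Under the label for indirect costs in the same entry: "Non-healthcare costs will be limited to loss of productivity using a human capital approach". Paid work is valued at the mean provincial wage. Time lost by retired people, and time lost from unpaid roles such as homemaking and caregiving, is valued at the Ontario and BC minimum wage.
- **Costs the participant incurs.** Just before that limit, under sources of direct cost data, the entry says that participants also report what they spend because of their back pain, including help with personal care, the house, shopping and travel.
- **Assistance data.** "Assistance required: using self-report data from follow-up surveys: paid and unpaid assistance required". In the analysis section, "assistance required (hours of paid assistance, hours of unpaid assistance) due to LBP" is compared between arms as a rate ratio.

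**The concern.** A societal cost should reflect the resources used whoever provides them, unless the plan states a narrower scope. Here the trial measures hours of unpaid help, but the cost rule gives them no place. If the care model changes disability, it could also change how much help relatives and friends give. Under the rule as written, any such difference would be absent from the incremental cost, the cost per QALY and the net benefit.

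There is also a plain drafting problem. Paying someone to do housework or to drive to an appointment is not a healthcare cost and is not lost productivity. The entry collects these payments as costs and then, a few sentences later, restricts non-healthcare costs to productivity. Two analysts could build different societal totals from this text. Settling the question after the hours have been seen would leave room for the analytic bias that the Introduction says the published plan is meant to reduce.

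**Working it through.** The documents give no total cost, wage rate or expected hours of assistance, so there is no figure to reproduce. The check is whether each collected item has both a place in the cost definition and a unit value.

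**Step 1: the plan's cost identity** (Costs entry)

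Total cost = direct healthcare costs + (participant's lost time × wage)

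**Step 2: each item against the identity**

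| Item | Quantity collected? | Unit value stated? | In total cost as written? |
|---|---|---|---|
| Healthcare services and medications | Yes | Yes (fee schedule, formulary, self-reported expense) | Yes |
| Participant's lost paid work | Yes, days | Yes, mean provincial wage | Yes |
| Participant's lost homemaking, volunteer or educational time | Yes, days | Yes, minimum wage | Yes |
| Paid assistance and transport | Yes, hours and expense | Yes, self-reported expense | Contradictory: listed among direct cost data, then shut out by the limit |
| Unpaid assistance | Yes, hours | None found | No |

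**Step 3: the other sections.** The Economic evaluation section repeats the rule as resource use times unit cost, or lost days times wage, and adds no value for a helper's time. The Process evaluation analysis splits any difference in total costs into healthcare use and missed occupational activities, and does not name assistance. Neither fills the gap.

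**Step 4: effect on the result.** Let ΔH be the between-arm difference in mean unpaid hours per person and w the value of an hour.

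- Omitted incremental cost = ΔH × w
- Shift in incremental net benefit if the hours were costed = −ΔH × w, the same at every willingness-to-pay value because only the cost side changes

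The documents give neither ΔH nor w. With both assumed:

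| Assumed ΔH (hours per person over the year) | At 15 dollars | At 18 dollars |
|---|---|---|
| 10 | 10 × 15 = 150 | 10 × 18 = 180 |
| 25 | 25 × 15 = 375 | 25 × 18 = 450 |
| 50 | 50 × 15 = 750 | 50 × 18 = 900 |

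The sign depends on which arm receives more help.

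**Step 5: overlap.** When a relative does housework that the participant cannot do, the participant's lost homemaking time is already priced. Missed activity is recorded in days and assistance is analysed in hours. No section describes hours split by task or tied to particular lost days, so an exact matching rule may not be workable. For participant i, let C be the cost without unpaid hours, H the unpaid hours, and m = 1 if any lost homemaking time is reported (0 if not):

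- Version A: C
- Version B: C + w × H
- Version C: C + w × H × (1 − m)

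For each participant, a cost with the overlap correctly removed lies between versions C and B. The between-arm difference is also bracketed if the overlapping share of hours is similar in the two arms.

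**The case against.** The best case for the plan has four parts.

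1. **Ambiguity.** The limiting sentence sits under the indirect-cost label and may be meant to bound only that category. The help listed under direct cost data might include unpaid hours, and the word caregiving in the minimum-wage rule might mean a helper's time. These readings are possible but strained. Free help is not an expense of the participant. Caregiving appears in a list of activities from which time is lost, while help received is a separate outcome. If either reading is intended, the plan still has to say so and give the unit value.
2. **Deliberate scope.** Leaving informal care out may be a pre-specified choice applied equally to both arms. The hours are reported in any case, and costs are to be shown disaggregated. This stands: the exclusion is not an error in itself, but then the scope should be stated.
3. **Overlap.** A reader might infer that the plan prices the same hour when the patient loses it but not when a relative gives it. The documents do not support that in general. For housework, shopping and meals, the loss may already be priced once through the participant's homemaking time. The clear gap is narrower: personal care, finances, transport, and help not matched by reported lost homemaking time.
4. **Size.** Both inputs to the dollar range are assumed, and nothing in the documents shows that the cost-effectiveness conclusion would change. This stands in full.

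**Conclusion.** The point holds as a gap and a contradiction in the cost definition. Followed as written, unpaid assistance hours contribute nothing to the primary societal cost, and the treatment of paid assistance and transport is inconsistent within one entry.

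A reader might go further and conclude that the sponsor has chosen to value informal care at zero, or that the societal result is biased by a known amount. The documents support neither. The zero is a consequence of the rule and is nowhere stated as an intention. The 150 to 900 dollars per person rests wholly on assumed hours (10 to 50) and assumed hourly values (15 to 18 dollars), and its direction is unknown.

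The societal perspective is primary only within the economic evaluation. The RMDQ primary outcome, its analysis and its power are unaffected. This is a cheap improvement.

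**What to change.** 1. Replace the limiting sentence with one stating that societal costs comprise direct healthcare costs, productivity loss, and paid assistance and transport costs.
2. Pre-specify the societal result with and without unpaid assistance hours, valued at the provincial minimum wage already used for homemaking and caregiving time.
3. Handle overlap by bounding it: one version adds all unpaid hours, and one adds none for participants who report lost homemaking time. Report both beside the version without unpaid hours.
4. Say which version is the base case. If unpaid care is deliberately left out of it, state this and describe the perspective as a restricted societal one.

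The cost is revised wording, one extra cost line and two further runs of the societal model, all from data already being collected. The plan says analysis starts only after data collection ends, and it provides an amendment route through the trial registry, so the change can be recorded before analysis begins. The downside is possible partial double counting in the version that adds all hours; comparing the versions shows how much it could matter.

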### **Implementation Measures:**

The following measures will be used to assess how the PT-led primary care model and usual physician- or nurse practitioner-led primary care model were implemented.

**Timely access to LBP care:** using the percentage of patient participants with LBP who are assessed within 48 hours of calling for an appointment. Participants who learned about the study and were invited to participate during an appointment for their LBP will not be included in this analysis.

**PT as the first point of contact:** using the percentage of patient participants with LBP in the PT-led primary care arm who visited a PT as their first point of contact for the current episode of LBP.

**Access to PT services:** using the percentage of patients who are classified as medium or high risk on the STarT Back screening tool who access PT (as endorsed by guidelines).

**LBP management:** using the following data being collected from the EHR to describe the LBP management provided to patient participants in each arm: education; exercise; psychological approaches; referrals to other primary care team members (e.g., primary care physicians, nurse practitioners, nurses, social workers, occupational therapists, group programming); referrals made to health professionals outside of the primary care team; medications prescribed, deprescribed, and suggested; diagnostic imaging ordered; lab work ordered and received; notes to employers or insurers; interprofessional communications with the primary care team; and other interventions provided.

**Patient adherence to recommendations:** adherence to recommendations from the primary care PT is being collected at the 6-week follow-up. For patient participants identified as medium- or high-risk using the STarT Back classification, whether or not they accessed recommended PT (either through a referral to a community PT or through the PT in primary care) is being collected as part of our health utilization survey questions.

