**Providing Additional PT Care to People with an Unmet Need:** The PT provides additional care at the primary care site for patients who are appropriate for PT (based on STarT Back score) and who have barriers to accessing PT care in their community. For example, people who may benefit from physiotherapy but do not have access to services—due to a lack of private or government insurance coverage or because of geographic or transportation barriers—are offered additional physiotherapy care. Care includes evidence-based, guideline consistent management, such as individualized education exercise behavioural approaches. To avoid duplication of available PT services, patient participants with private or government funded health insurance for PT are referred to external PT services.

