therapies, spinal manipulation, massage, operant therapy, cognitive behavioural therapy, non-steroidal anti-inflammatory drugs, topical cayenne pepper, and multicomponent biopsychosocial care. Interventions that are recommended against include: traction, ultrasound, transcutaneous electrical nerve stimulation, and lumbar supports. Additionally, referrals for diagnostic imaging or physician specialist visits for spinal injections or surgery consultations are rarely needed for LBP and thus will be compared between arms for a potential reduction in low-value care. The intended implementation outcome is that patient participants receive care recommended in practice guidelines and do not receive care recommended against in practice guidelines, and that a low proportion of people receive *referrals or prescriptions* for diagnostic imaging, physician specialist, or medications outside of NSAIDs. Receipt of each intervention recommended by the guidelines, recommended against by the guidelines, and referrals (for imaging, spinal injections, or surgical consults) will be presented as incidence rates with confidence intervals and compared by calculating relative risks with confidence intervals using GEE-type robust variance estimates, accounting for clustering, using an exchangeable working correlation matrix. We will use empirical covariance (“sandwich”) bias-adjusted (residual-based) estimators and the Fay and Graubard correction to account for small number of clusters. We will incorporate the same covariates as with our effectiveness analysis.

5) Describing adherence to PT primary care recommendations. The intended implementation outcome is that patient participants report actioning the initial recommendations for physical activity and exercise and that those who were recommended to access PT services report doing so.

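### Item 4 compares receipt of guideline care using the primary care record alone; for education, exercise and psychological content, fuller recording in the PT-led arm probably biases the relative risk towards it

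*Combined protocol and SAP*

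**What the plan says.** Under Implementation Measures, LBP management is measured "using the following data being collected from the EHR to describe the LBP management provided to patient participants in each arm". The list that follows covers education, exercise, psychological approaches, prescriptions, imaging orders and a catch-all for other interventions. For care elsewhere, the listed item is "referrals made to health professionals outside of the primary care team".

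Under Process evaluation analysis, item 4 analyses "Receipt of each intervention recommended by the guidelines, recommended against by the guidelines", plus certain referrals, as relative risks with confidence intervals. Its stated aim is about patients: "The intended implementation outcome is that patient participants receive care recommended in practice guidelines". The ten recommended interventions include needling "therapies, spinal manipulation, massage, operant therapy, cognitive behavioural therapy". Traction, ultrasound, TENS and lumbar supports are on the recommended-against list. Item 4 names no data source beyond the record.

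Under Health System and Societal Outcomes, visits to outside physiotherapists, chiropractors, massage therapists and others are collected in both arms "using self-report data from follow-up surveys cross checked with reports the electronic health record when possible". They serve the utilization outcome and are not linked to item 4.

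**The concern.** Item 4 is worded as what patients received, but its data are what the primary care team charted. The two differ when treatment is given outside the team, and the shortfall need not be the same in both arms.

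The design creates such a difference. Sites that already had a PT were excluded, so at entry no usual-care site had one in the team. PT-led sites were given one, whose care presumably goes into the record being extracted. A usual-care patient who is referred to community PT and exercises there appears in the listed items as a referral without exercise.

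At stake is the guideline-alignment comparison in item 4. Also at stake are the exploratory STarT Back hypotheses at the end of the process evaluation plan, which expect medium- and high-risk PT-led patients to have management closer to guidelines. Part of an apparent advantage could be a recording difference.

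**Working it through.** The plan states no figure for this measure, so there is nothing to reproduce. The check is a reading of the text followed by a hypothetical calculation.

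**Where each type of care is delivered**

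- PT-led arm: every participant was offered an initial PT assessment (Duration of Treatment Period). The brief intervention, with tailored exercise, advice and cognitive reassurance, is given at that visit (Index Intervention). High-risk patients are matched to the in-team PT, who has training in psychosocial risk factors. For those with access barriers, "The PT provides additional care at the primary care site for patients who are appropriate for PT".
- PT-led arm, outside care: patients with PT insurance are sent to external services, and medium-risk patients are matched to community PT.
- Usual care: no PT in the team at entry. In the pilot 23% were referred to PT and 5% to massage therapy. Other treatment is unrestricted in both arms.

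**Formula.** Let true receipt be equal in both arms. Let f be the share of receipt that occurs only outside the team, and s the probability that the record shows such care. Assume in-team care is fully recorded and there are no false entries. Then

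apparent RR = [1 − f_PT(1 − s)] / [1 − f_UC(1 − s)].

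The documents give none of f_PT, f_UC or s.

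**Illustration (assumed values).** True receipt is 40% in each arm. In usual care 23 points come only from outside, borrowing the pilot referral rate, so f_UC = 0.23/0.40 = 0.575. Recorded usual-care receipt is 0.17 + 0.23s. If x is the PT-led receipt obtained only outside, recorded PT-led receipt is (0.40 − x) + xs.

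| PT-led receipt only outside (x) | s = 0 | s = 0.25 | s = 0.5 | s = 0.75 |
|---|---|---|---|---|
| 0 points | 0.40/0.17 = 2.35 | 1.76 | 1.40 | 1.17 |
| 10 points | 0.30/0.17 = 1.76 | 1.43 | 1.23 | 1.09 |
| 23 points | 1.00 | 1.00 | 1.00 | 1.00 |
| 30 points | 0.10/0.17 = 0.59 | 0.77 | 0.88 | 0.95 |

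The true relative risk is 1.00 in every cell. At s = 1 every row returns 1.00.

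**Which row applies to which item**

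- *Education and exercise.* A relative risk implies ever/never scoring. A PT-led patient who attends the first visit then already counts, and later community PT adds nothing. Only patients who get this care solely outside are missed, so x should be small and the upper rows are more plausible.
- *Psychological content.* The same reasoning applies through first-visit reassurance and in-team care of high-risk patients.
- *Massage and manipulation.* These lie mostly outside the team in both arms. If capture is equally poor, the relative risk is imprecise but not biased. The direction is otherwise unknown.
- *Recommended-against items.* Unseen outside use makes an arm look better. If usual-care patients get more of their physical treatment outside, the error flatters usual care.
- *Imaging, specialist referral, prescriptions.* These are ordered through the chart in both arms, so the mechanism does not apply.

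**The case against.** The strongest reply is that the measure concerns the team. Implementation Measures is introduced as showing how each care model was carried out, and item 4 begins by speaking of management provided. On that reading the record is the right source. This has force, but item 4 then states both its analysis and its aim as receipt by patients, so the wording would still need correcting.

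A second reply is that PT-led patients are also referred out, so the direction is open. This stands for the item 4 list as a whole: the table runs from 2.35 down to 0.59. It carries little weight for education and exercise, because the in-team visit comes before any onward referral.

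A third is that outside care is reported elsewhere. The utilization analysis compares outside provider visits, and item 3 compares PT access in medium- and high-risk patients, for whom uptake of recommended PT is asked in the utilization survey. This softens the problem, since a careful reader could see usual-care patients' outside PT. It does not correct the item 4 ratios. The catch-all for other interventions and outside reports reaching the chart may also give some capture.

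A reader might infer that every item 4 relative risk favours PT-led care, or that 23 percentage points of usual-care PT treatment go unrecorded. The documents support neither. The direction differs by item, and 23% is a pilot referral rate, not a measure of treatment received or of treatment missing from the chart.

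**Conclusion.** The concern holds for a defined part of item 4. Receipt by patients is compared using a source whose listed items record outside referrals but not outside treatment. For education, exercise and psychological content, ascertainment is likely more complete in the PT-led arm, so the relative risk for receipt is likely biased towards PT-led care. This assumes that the in-team PT charts this care and that most PT-led participants attend the initial visit. For massage, manipulation and recommended-against items, the direction is unknown or may run the other way.

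No size can be stated. The ratios above rest on assumed shares and on equal true receipt, a constructed null for a model designed to deliver exercise.

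A reader might extend this to the mechanism claims generally. The mediation analyses use PSEQ, PHQ-2, PCS and TSK-11, not guideline receipt, so they are untouched, as are the primary outcome and the survey-based utilization outcomes. The affected conclusions are the item 4 guideline-alignment comparison and the STarT Back subgroup hypotheses about it, which the plan itself calls exploratory and likely underpowered.

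**What to change.** Amend item 4 before analysis starts, using the plan's own amendment route:

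1. For items that provider type can reasonably proxy, such as massage and manipulation, define receipt in both arms as recorded in the EHR or self-reported on any follow-up utilization survey. Report an EHR-only sensitivity analysis.
2. For education, exercise and other content visible only in notes, keep the planned relative risks but define and report them as care documented as provided by the primary care team. Draw no conclusion about total receipt. Present them beside the survey-based outside-visit results and the PT-access comparison in item 3.
3. Leave imaging, specialist referral and prescription items EHR-based.

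The cost is outcome wording and a merge of two datasets already being collected. The downsides are recall error and the fact that provider type only approximates content: a chiropractic visit does not prove manipulation, and a PT visit does not reveal what was done. No planned between-arm comparison is lost.
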